9.6. Data Management

We will collect electronic primary care patient records from the CPRD in the UK and electronic records on inpatient and outpatient admissions and dispensation of drugs in Sweden from the NPR and PDR. Routine procedures will include checking electronic files, maintaining security and data confidentiality, following analysis plans, and performing quality-control checks of all programmes. In Spain, SIDIAP will be in charge of the data management.

Each database custodian will maintain any patient-identifying information securely on site according to internal standard operating procedures. [REDACTED] will maintain the data cuts according to internal procedures.

An [REDACTED] data analyst will write and review programs to implement the analyses outlined in the Data Analysis section below. The project team will review all data output, including SAS® code as needed. Changes and corrections to programs stemming from the review will be made as appropriate. All programs will be saved and the process documented. Security processes will be in place to ensure the safety of all systems and data. Every effort will be made to ensure that data are kept secure so that they cannot be accessed by anyone except select study staff.

Appropriate data storage and archiving procedures will be followed (i.e., storage on compact disk read-only memory [CD-ROM] or digital versatile disk [DVD]) with periodic backup of files to tape. Standard procedures will be in place at each research centre to restore files in the event of a hardware or software failure.

9.7. Data Analysis

Analyses will be performed in each of the study countries separately.

9.7.1. Patient Characteristics and Medical History

At linaclotide cohort entry date or index date, the socio-demographic characteristics of all linaclotide users, comorbidities, and the most relevant co-medications will be assessed by reviewing data for a minimum of 12-months prior to index date, and summary statistics will be reported with mean and standard deviation for continuous variables and number and percentage for categorical ones. The number and proportion of patients with missing data will be reported for each of the variables of interest.

Baseline characteristics will also be described in the following subgroups of patients, selected because in the clinical development programme, the use of linaclotide in these groups reflected important missing information, potential off-label use, and potential for abuse/excessive use:

- Children and adolescents (younger than 18 years of age)
- Older adult population (65 years or older)
- Pregnant or breast-feeding women

- Male patients
- Non-IBS-C patients with chronic constipation
- Patients with known or suspected mechanical gastrointestinal obstruction or IBD
- Patients with specific comorbidities (i.e., hepatic or renal impairment, cardiovascular diseases and associated risk factors, hypertension, diabetes)
- Patients with potential for abuse/excessive use—e.g., use for weight loss (patients with body mass index <20), use as a laxative (patients with codes for constipation only).

9.7.2. *Linacotide Prescription Patterns*

Linacotide treatment patterns will be assessed in the follow-up period from index date, as defined above.

The numbers and proportions of patients who experience one of the following treatment events will be reported separately:

- Discontinuation in the prescription of linacotide
- Switching from linacotide prescription to the prescription of another drug (i.e., laxatives, antispasmodics, prokinetics or antidepressants)

Switching from linacotide requires discontinuation in the prescription of linacotide but these patients will be allocated to switching so the two categories will be mutually exclusive. Kaplan-Meier estimates will be used to describe the times to first discontinuation or switching.

To better assess differences in time to event by the alleged reason for linacotide prescription (IBS-C or other conditions), Cox regression analysis will be employed. Multivariate Cox regression models will be fitted to identify the effects of the indication and various other baseline variables on the time from initiation of linacotide to first treatment discontinuation or switching. For each of the two outcome variables (time to discontinuation and time to switching), a set of plausible candidate models will be proposed and fitted to the data. Models will be ranked according to Akaike's Information Criterion and the best model will be selected; or, if several models prove to perform well, these will be averaged to produce a final model. Some iteration between choosing candidate models and data analysis will likely be necessary, owing to the need to check that the proportional hazards assumption holds for each candidate model.

Statistical analyses will be conducted using SAS® statistical software.

9.8. **Quality Control**

Standard operating procedures at each research centre will be used to guide the conduct of the study. These procedures include internal quality audits, rules for secure and confidential data storage, methods to maintain and archive project documents, quality-control procedures for programming, standards for writing analysis plans, and requirements for senior scientific review.

All work will be subject to quality control and documentation procedures to make certain the final report is accurate and thorough and the analyses can be reproduced. If the data do not permit an analysis as planned (e.g., through insufficient sample size in a subgroup analysis) or if clarifying analyses are required (e.g., an unexpected result that could be explained by a subgroup analysis), [REDACTED] staff will inform Allergan and include the additional information and results in the report. All key study documents, such as the analysis plan, abstraction forms, and study reports, will undergo quality-control review, senior scientific review, and editorial review.

A quality-assurance audit of this study may be conducted.

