4.8. Study Size

Based on projected post-authorisation usage information provided by Almirall [MAH of linaclotide at the time of development of this protocol] in the linaclotide risk management plan (RMP), sales data and additional assumptions on the distribution of patients and treatment discontinuation, we estimated that by December 2016, roughly 2,674 patients using linaclotide could be captured by the proposed database in the UK, 2,407 in Spain, and 4,584 in Sweden. Overall, this represents over 9,650 patients who would have been exposed to linaclotide in the three target databases), assuming Almirall [MAH of linaclotide at the time of development of this protocol] sales forecasts are correct, and a combined exposure of approximately 4,572 patient-years. In the progress report for 2016, users of linaclotide included in each of the study database were reported to be below the targeted numbers. Following the recommendation of the PRAC rapporteur, the end of the data collection was then extended by one year until December 2017.

The extended time frame is considered adequate to achieve the estimated sample to conduct the linaclotide DUS and to allow for sufficient follow-up to assess long-term use of linaclotide and use by subgroups of interest.

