8.2. Operational Objectives

- To describe the characteristics of patients prescribed linaclotide at time of first prescription (defined as socio-demographics, comorbidities (up to 15), co-medications (up to 15), and other potential variables of interest (up to 10))
- To also describe characteristics of patients by specific subgroups of interest (e.g., paediatric population, elderly population patients with diabetes, hypertension, or cardiovascular disease diagnostic codes, patients with codes for constipation only)
- To estimate the number and percentage of patients with the potential for linaclotide off-label use in the following groups: off-label/abuse/excessive use as a laxative due to the pharmacology of linaclotide within patients with eating disorders; off-label use in other types of constipation disorders distinct from IBS-C, particularly in the elderly population; and potential for off-label use in the paediatric population for chronic constipation.
- To describe the proportion and characteristics of patients prescribed linaclotide (overall and by alleged indication) who experience any of the following:
 - o Discontinuation of linaclotide (permanently during the observation period)
 - o Switching from linaclotide to drugs potentially also used by patients with IBS-C moderate to severe: laxatives, antispasmodics, prokinetics, or antidepressants (Hugin, 2003)
- To describe the duration of linaclotide treatment until discontinuation or switching

- To describe the effect of the indication (IBS-C diagnosis versus other) on the time from initiation of linaclotide to discontinuation or switching

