projected number of patients	518	1211	2,674
projected number of patients-years	211	557	1,219
SIDIAP: 12.8% of Spain			
projected number of patients	207	1,108	2,407
projected number of patients-years	76	456	1,122
Sweden National Patient Register: 95% of Sweden			
projected number of patients	1,147	2,766	4,584
projected number of patients-years	506	1,250	2,231
Combined:			
projected number of patients	1,872	5,085	9,665
projected number of patient-years	794	2,263	4,572

*86% in Sweden and Spain, 81% in the UK, of the total number of linaclotide users
Abbreviations: CPRD=clinical practice research datalink; UK=United Kingdom

By the end of 2016 it was estimated that over 9,650 patients would have been exposed to linaclotide

in the three target databases together, for a combined exposure of more than 4,500 patient years. The UK would be contributing approximately 28% of patients, Spain 25%, and Sweden 47%.

For the treatment patterns, a total of approximately 8,800 patients would allow the detection of a hazard ratio of 1.2 or greater for patient characteristics, assuming linaclotide discontinuation or linaclotide switching occur in about 10% the observed sample (users with a specific characteristic) with a probability of 40%, with 90% power and a two-sided type I error rate (alpha) of 5%.

In the progress report for 2016, users of linaclotide included in each of the study databases were reported to be below the targeted numbers. Following the recommendation of the PRAC rapporteur, the end of the data collection was then extended by one year until December 2017 to allow for the number of users to reach the desired sample size.

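### The indication effect, a named secondary objective, is to come from AIC-ranked or averaged Cox models that may be revised during analysis, with no stated rule keeping indication in every model

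*Protocol*

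**What the plan says.** Section 8.2 of the protocol lists as an operational objective: "To describe the effect of the indication (IBS-C diagnosis versus other"), on the time from starting linaclotide to discontinuation or switching. Section 9.3.3 makes these two times secondary endpoints.

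Section 9.7.2 says Cox regression serves to assess differences by the alleged reason for prescription, and that multivariable models will address indication together with other baseline variables. A set of candidate models is to be proposed for each of the two outcomes. Then: "Models will be ranked according to Akaike's Information Criterion and the best model will be selected". If several models do well, they are averaged instead. The section goes on: "Some iteration between choosing candidate models and data analysis will likely be necessary", because proportional hazards must be checked for each candidate. Section 4.9 says that more complex models, including interactions with time, will be proposed if the assumption fails.

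On the unit of analysis, section 9.7 says: "Analyses will be performed in each of the study countries separately". Section 4.9 adds pooled analyses, but only for the primary objectives; treatment patterns are secondary.

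**The concern.** The objective asks for the size of one named contrast. AIC ranking serves a different purpose, finding a model that predicts well, and a model can predict well without the term the objective is about. Nothing in section 9.7.2 requires indication to be in every candidate, and the candidate set may change while the data are being analysed.

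Two things follow if indication competes with the other variables. In some analyses the chosen model contains no hazard ratio for indication. In the rest, the reported hazard ratio is one that passed a threshold, so on average it lies further from 1 than the truth. Averaging does not remove the problem by itself: if models without indication enter the average with a zero coefficient, the effect shrinks. The protocol does not say when averaging replaces selection, nor how the interval allows for either.

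Three countries and two outcomes make six separate selections. They can end with different covariate sets, so the indication hazard ratios would not be adjusted alike across countries.

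**Working it through.** **Inputs.**

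- Section 4.8 projects "roughly 2,674 patients using linaclotide could be captured by the proposed database in the UK, 2,407 in Spain, and 4,584 in Sweden".
- Section 9.5 states that "a total of approximately 8,800 patients would allow the detection of a hazard ratio of 1.2 or greater for patient characteristics". The other inputs it gives are a 10% share of users having the characteristic, a 40% event probability, power of 90% and two-sided alpha of 5%.
- Assumed: the share q of users in the smaller indication group. The 10% in section 9.5 refers to a generic patient characteristic, so 10%, 30% and 50% are shown.

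**Reproducing the protocol's figure.** By Schoenfeld's formula, events = (1.960 + 1.282)² / [(ln 1.2)² × 0.1 × 0.9] = 10.507 / (0.03324 × 0.09), which rounds up to 3,513. Patients = 3,513 / 0.40 = 8,783, which matches the stated 8,800. So the protocol's figure means 10% with the characteristic and a 40% event probability. It is a total over all three databases, whereas the indication models are fitted by country.

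**When AIC drops a term.** AIC keeps a one-degree-of-freedom term when its likelihood-ratio chi-square exceeds 2, that is |z| > √2 = 1.414, or p < 0.157.

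**Formulas.** SE = 1/√(0.4 N q(1−q)); expected z = μ = ln(HR)/SE; P(drop) = Φ(1.414 − μ) − Φ(−1.414 − μ). The mean of z when kept is μ + [φ(1.414 − μ) − φ(1.414 + μ)] / P(keep). Multiplying by SE and exponentiating gives the average retained hazard ratio.

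**UK, q = 10%, HR 1.2.** 2,674 × 0.4 = 1,069.6 events; × 0.09 = 96.26; SE = 0.1019; μ = 0.1823/0.1019 = 1.789. P(drop) = Φ(−0.375) − Φ(−3.203) = 0.353. Mean z when kept = 1.789 + 0.3695/0.6467 = 2.360, and exp(2.360 × 0.1019) = 1.27.

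| Country (N) | q | μ at HR 1.2 | P(drop) | Mean HR when kept |
|---|---|---|---|---|
| UK (2,674) | 10% | 1.79 | 35.3% | 1.272 |
| UK | 30% | 2.73 | 9.4% | 1.215 |
| UK | 50% | 2.98 | 5.9% | 1.209 |
| Spain (2,407) | 10% | 1.70 | 38.8% | 1.283 |
| Spain | 30% | 2.59 | 11.9% | 1.219 |
| Spain | 50% | 2.83 | 7.9% | 1.212 |
| Sweden (4,584) | 10% | 2.34 | 17.7% | 1.230 |
| Sweden | 30% | 3.58 | 1.5% | 1.202 |
| Sweden | 50% | 3.90 | 0.6% | 1.201 |

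**Other cases.**

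- With no true effect, the term is dropped 84.3% of the time. When kept, its nominal 95% interval covers the truth 68.2% of the time.
- At HR 1.2, coverage when kept is about 96 to 97% by the same approximation.
- Section 9.7.2 makes discontinuation and switching mutually exclusive and models each. If the 40% covers both and splits evenly (an assumption), 20% events per outcome gives drop rates in the UK and Spain of about 56% and 58% at q = 10%, and 24% and 28% at q = 50%.

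**If indication is always kept.** A simulation used 1,500 runs per setting, the countries' event counts (1,070, 963 and 1,834), eight adjusters, backward AIC and a linear-normal approximation to the Cox model. With indication forced in and AIC choosing only the adjusters, coverage was 93.7 to 94.8%. A fixed full model gave 94.1 to 95.2%. The loss was under one point in every setting.

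**The case against.** The strongest reply is that section 9.7.2 names indication as the reason for fitting the models, so a sensible analyst would keep it and let AIC choose among the other variables. On that reading the harm is under one coverage point. This is a fair reading, but the text does not require it: indication is listed alongside other baseline variables, and the selection rule exempts none of them.

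Second, the iteration is tied to the proportional hazards check. It is not described as a search for better fit, and a reader who infers one goes beyond the text. What stands is that the check needs no new covariate set, since section 4.9 already answers failure with time interactions.

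Third, averaging may apply exactly where indication is borderline. That is true, and the drop probabilities above cover only the single-winner branch.

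Fourth, Annex 1 lists a separate SAP (version 1.1), not seen here, which may fix the candidates and the forced terms. Their absence from the protocol would not be a fault by itself. The point rests on the selection method that the protocol does state.

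Fifth, the objective is secondary, the study is declared descriptive with no prior hypothesis, and the 10% share is not specific to indication. All of this is accepted and limits the weight of the point.

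**Conclusion.** The point holds as a cheap improvement. The protocol states a selection procedure for an objective that needs an estimate, and that procedure permits the estimate to be omitted or exaggerated.

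Its size depends on the unknown indication split. At HR 1.2 and 40% events the chance of omission runs from about 6% to 39% in the UK and Spain and from about 1% to 18% in Sweden. Average inflation runs from negligible to a retained hazard ratio of 1.28. Section 9.5 reports that user counts were below target in every database in 2016. If the year's extension did not make this up, the drop rates would be higher than shown.

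Three stronger conclusions are tempting but unsupported:

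- **Indication will be dropped.** The protocol permits this by silence and does not say it.
- **The interval ignores selection and is too narrow.** The protocol does not say how the interval is formed. At HR 1.2 coverage among retained estimates is close to nominal; the marked shortfall appears when there is no true effect.
- **The objective would be left with no information.** Section 8.2 separately plans the proportions discontinuing or switching by alleged indication, and these remain whichever Cox model is chosen.

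The harm is a missing or biased estimate. It is not a confirmatory type I error. The sample size calculation reproduces and is unaffected.

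**What to change.** In section 9.7.2:

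1. State that indication (IBS-C versus other) is in every candidate model and in every averaged model.
2. For each outcome and country, report the indication hazard ratio from one adjustment set chosen from the section 9.3.2 variables before outcome data are analysed. The set need not contain all of them.
3. Restrict AIC selection or averaging to secondary exploration of other predictors. Define when averaging applies, and use unconditional standard errors if it does.
4. Let the proportional hazards check add a time interaction, but not change the covariate set.

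The cost is wording in the protocol, with the SAP aligned to it, and slightly wider intervals than a model trimmed by AIC would give. The required size stays at about 8,783 patients by the protocol's own formula.

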9.9. Limitations of the Research Methods

Categorisation of patients with IBS into IBS-C, IBS-D, or IBS-M might be challenging. Differentiation between IBS-C and chronic constipation will also be challenging. As a consequence, some degree of misclassification is to be expected.

The use of over-the-counter medications for the treatment of IBS-C-related symptoms, constipation, and diarrhoea is acknowledged as another study limitation (Hungin, 2003). Over-the-counter medications will not be available in the UK or in Sweden. For Spain, we will include over-the-counter medications; however, we expect under-recording of these in the database.

The CPRD provides a large, diverse, and representative sample of UK people using primary care services, which allows for generalizability of the study findings to the broader UK population. The CPRD (and its predecessor General Practice Research Database [GPRD]) have been widely used for observational studies, with over 890 studies published to date in peer-reviewed journals. The SIDIAP database includes information for 90% of the population resident in Catalonia, a region in the north-east of Spain, and resembles the data collected by UK databases. One limitation is that date of prescription is available for only the first prescription and, thereafter, only approximate date of dispensation is available. For Sweden, the NPR and PDR cover the entire Swedish population and have been previously used in observational studies including drug utilisation ones. However, no primary care data will be available, so diagnoses will be those determined by a specialist, which are expected to be required for the variables of interest for this study. The PDR is not complete with regard to drugs used in nursing homes. According to the National Board of Health and Welfare, about 1% of people aged 65–79 years live in nursing homes, and about 20% of people aged 80 or more years live in nursing homes in Sweden [Socialstyrelsen]. This may be reflected in potential lower numbers of elderly patient using linaclotide identified in Sweden.

The validity of research findings based on CPRD data as well as the other databases depends on the quality and completeness of data recorded. We are only able to identify comorbidities for which the patient has consulted their GP. Referrals are not always uniformly coded and may appear as free-hand text or letters within the database.

Interval censoring might have an impact on the precision of the results.

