Information on diagnoses will be obtained from the Swedish NPR, which covers all public inpatient care since 1987 and all outpatient visits since 2001. The medical data include main and up to 21 secondary diagnoses and up to 30 surgical procedures from public and private service providers (National Board of Health and Welfare (Sweden), 2012). Diagnoses are coded using ICD-10 codes and surgical procedures with the Nordic Classification of Surgical Procedures. Primary care is not yet covered in the NPR. At present, the NPR is updated once a year.

Information about treatment use will be obtained from the Swedish PDR. Its coverage is close to 100% of all prescribed medicines from both primary health care centres and outpatient specialists dispensed to the Swedish population, and information is available since July 2005 (Wettermark et al., 2007). The register contains data on the substance, brand name, formulation, and package, dispensed amount, dosage, expenditure, and reimbursement as well as date of dispensing. Dispensation of over-the-counter (OTC) medications is not included.

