Administrative data from inpatient hospital admissions and outpatient visits; and 4. Medical data regarding main and up to 21 secondary diagnosis using the ICD-10 classification, external cause of injury and poisoning, and up to 30 surgical procedures from public and private service providers. A quality control check of the NPR is performed periodically, and in 2007 the main diagnosis was missing from 1.0% of records. At present, the NPR is updated once a year.

Proposed Data Source: The Prescribed Drug Registry

The Swedish Prescribed Drug Register (PDR) has been functioning since July 2005 and contains data on all prescriptions dispensed to the entire Swedish population. Data collection is administered by the National Corporation of Swedish Pharmacies, a state-owned company responsible for the provision of pharmaceutical services to the whole country. Information from all prescriptions dispensed is transferred monthly to the National Board of Health and Welfare, which is responsible for maintaining the PDR.

The register contains the following data on drugs prescribed and dispensed in ambulatory care: dispensed item (substance, brand name, formulation, and package); dispensed amount, dosage, expenditure, and reimbursement; age, sex, and unique identifier (personal registration number) of the patient; place of residence of the patient (county, municipality, and parish); date of prescribing and dispensing; the practice (primary health care centre or hospital clinic) that issued the prescription; and the prescriber's profession (e.g., general practitioner; specialist in internal medicine, psychiatry, or paediatrics). All drugs are classified according to the ATC classification system. The register does not include data on over-the-counter (OTC) medications or drugs administered in hospitals or complete data on drugs that are used in ambulatory care but are administered during day care at hospitals. The register is not complete with regard to drugs used in nursing homes.

Italy

In Italy, data sources have limited reference population size or limited availability of variables relevant for the proposed study. Additionally, linaclotide sales in Italy started in September 2014 hence the sample size contributed by Italy is relatively small.

Excluded Data Source (Potential alternative): Health Search/CSD Longitudinal Patient Database

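### Sweden captures primary-care prescriptions but not primary-care diagnoses, so users never coded in specialist care fall into 'other' and bias the off-label and indication results in a direction that depends on the definition

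*Protocol*

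**What the plan says.** **Exposure.** Swedish cohort entry is by dispensation (Protocol 9.2.2.1). The Prescribed Drug Register (PDR) is described in 4.7 as covering "close to 100% of all prescribed medicines from both primary health care centres and outpatient specialists".

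**Diagnosis.** Swedish diagnoses come from the National Patient Register (NPR). Section 4.7 states: "Primary care is not yet covered in the NPR". Section 9.9 repeats this as a limitation: "no primary care data will be available, so diagnoses will be those determined by a specialist". It then says it expects specialist diagnosis to be needed for the study's variables anyway, and gives no figure or source.

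**Classification.** Section 9.3.4 identifies IBS-C by an IBS code combined with a constipation code. Under the ICD-10 rules in Annex 3 A (Table 5), a patient with an IBS code but no constipation or diarrhoea code is labelled IBS-M.

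**Use in the analysis.** Off-label use with regard to indication is a primary question (8.1). Section 8.2 sets the indication contrast as the "effect of the indication (IBS-C diagnosis versus other"), and 9.7.2 puts it into the Cox models. Section 4.9 plans aggregated three-country analyses for the primary objectives. On Sweden's weight, 4.8 projects "roughly 2,674 patients using linaclotide could be captured by the proposed database in the UK, 2,407 in Spain, and 4,584 in Sweden".

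**The concern.** The exposure net is wider than the diagnosis net. A person who was diagnosed and prescribed linaclotide only in primary care enters the Swedish cohort but cannot meet the IBS-C rule. With two levels, such a user can only be other. The commitment in 9.7.1 to report missing data does not help, because an absent diagnosis code reads as no diagnosis rather than as missing.

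The UK and Spanish sources hold primary-care diagnoses (4.7), so the gap is specific to Sweden. The general caveat in 9.9, that IBS subtypes and chronic constipation are hard to tell apart, concerns coding difficulty and does not cover it.

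A primary result is at stake: part of any country difference in off-label use would reflect how the registers are built. The same misclassification enters the main covariate of the discontinuation and switching models.

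**Working it through.** **1. The plan's own share.** From 4.8 and Table 3: 2,674 + 2,407 + 4,584 = 9,665. Sweden is 4,584 / 9,665 = 47.4%, the UK 27.7% and Spain 24.9%. This reproduces 9.5: "The UK would be contributing approximately 28% of patients, Spain 25%, and Sweden 47" per cent.

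**2. How current that share is.** It is the end-2016 projection, and collection now runs to December 2017. Multiplying the annual forecasts in Table 2 by the coverage in Table 3 (UK 8%, Spain 12.8%, Sweden 95%) gives:

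- 2016: UK 27,619 × 0.08 = 2,210; Spain 16,435 × 0.128 = 2,104; Sweden 3,263 × 0.95 = 3,100. Sweden = 3,100 / 7,413 = 41.8%.
- 2017: UK 45,279 × 0.08 = 3,622; Spain 23,073 × 0.128 = 2,953; Sweden 4,052 × 0.95 = 3,849. Sweden = 3,849 / 10,425 = 36.9%.

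These are annual rather than cumulative shares and rest on forecasts, but they suggest that Sweden's final weight may be below 47%.

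**3. Who is affected.** Section 9.3.2 searches the whole medical history for prior diagnoses, and 4.7 gives NPR inpatient data from 1987 and outpatient data from 2001. A primary-care prescription after an earlier specialist diagnosis is therefore classified correctly. The users lost are those who never received both codes in specialist care. This includes users with a specialist IBS code whose constipation was coded only in primary care: they become IBS-M, hence other.

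**4. If off-label means not IBS-C.** Let p be the true on-label share (assumed equal in all countries), f the share of Swedish on-label users without both specialist codes, and w Sweden's weight. Take the UK and Spain as error-free. The documents give neither p nor f.

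- Apparent Swedish off-label share = 1 − p(1 − f)
- Overstatement of the aggregate = w × p × f

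| True off-label (1 − p) | f | Sweden shows | Aggregate shows (w = 0.474) |
|---|---|---|---|
| 60% | 0.1 / 0.3 / 0.5 / 0.7 | 64 / 72 / 80 / 88% | 61.9 / 65.7 / 69.5 / 73.3% |
| 40% | 0.1 / 0.3 / 0.5 / 0.7 | 46 / 58 / 70 / 82% | 42.8 / 48.5 / 54.2 / 59.9% |
| 20% | 0.1 / 0.3 / 0.5 / 0.7 | 28 / 44 / 60 / 76% | 23.8 / 31.4 / 39.0 / 46.6% |

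The aggregate is overstated by 1.9 to 26.6 percentage points across this grid. At p = 0.6 and f = 0.3 the excess is 0.474 × 0.18 = 8.5 points; with w = 0.369 it would be 6.6.

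**5. If off-label is counted from positive codes.** Section 8.2 names eating disorders, other constipation disorders and paediatric chronic constipation. Section 9.7.1 names non-IBS-C patients with chronic constipation and patients with constipation codes only. Apart from age, these need a recorded diagnosis. Let q be the true share in such groups and f now the fraction of them uncoded in Sweden. Sweden shows q(1 − f), and the aggregate falls by w × q × f. For q = 0.4 and f = 0.3, Sweden shows 28% and the aggregate 0.526 × 0.40 + 0.474 × 0.28 = 34.3%. The bias is now downward. A partial exception is a user with a specialist constipation code whose IBS is recorded only in primary care: that user would be added wrongly to the constipation-only group.

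**6. Indication effect.** With p = 0.6 and f = 0.3, the fraction of Swedish 'other' users who are truly on-label is 0.18 / 0.58 = 31%. Such mixing pulls the Swedish contrast towards no difference if these users behave like coded IBS-C users. As a rough linear approximation, a hazard ratio of 1.2, the size 9.5 plans to detect, becomes 1 + 0.2 × (1 − 0.31) = 1.14.

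**The case against.** - **Direction.** A reader might infer that Swedish off-label use is simply inflated. The documents do not support that as the only outcome. The IBS-C versus other split is written for the time-to-event objective, while the off-label objective in 8.2 names groups that mostly need a positive code. The broader wording in 8.1 and 4.9 allows the not-IBS-C reading too. This objection stands: both directions are possible.
- **Reach.** A reader might infer that every user prescribed linaclotide in primary care is misclassified. The whole-history look-back rules that out, though it does nothing for users never coded in specialist care.
- **Weight.** The 47% is tied to the original horizon and may be too high. Pooling is stated in 4.9, whereas 9.7 and the Annex 2 comment mention only separate analyses, so the aggregate part rests on 4.9. Country results will also be visible on their own. These points reduce the aggregate problem and leave the Swedish estimate as it is.
- **Selection instead.** Section 9.2.1 defines the Swedish source population as patients registered in the NPR linked to the PDR. If that meant having an NPR record, users seen only in primary care would be excluded rather than called other. Entry by dispensation (9.2.2.1) and the claim of whole-population coverage (9.9) point against this, but the wording should be reconciled.
- **Disclosure and the SAP.** The missing primary-care data are disclosed, and coding detail often sits in the SAP, which is listed in Annex 1 but not at hand. However, the protocol itself fixes the data source, the code rules and the two-level contrast, and it makes the unsupported reassurance. Section 9.9 never links the gap to off-label use.

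**Conclusion.** The concern holds as an ascertainment gap of unknown size, with a direction that depends on how off-label is defined. Following the protocol as written, Swedish users without both qualifying specialist codes are placed in other. This biases the Swedish off-label estimate, the aggregate planned in 4.9 and the indication effect in the Cox models.

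The figures above are illustrations. They rest on assumed values of the true off-label share and the uncoded share, on equal true shares across countries, and on error-free classification in the UK and Spain. The bias is negligible only if very few Swedish users lack specialist codes, and the protocol offers no evidence for that.

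A reader might also conclude that the main Swedish estimate should be restricted to prescriptions issued by specialists. The documents do not support that: the research questions concern all users, place of issue is not place of diagnosis, and off-label use may differ between settings. The correction is a cheap improvement and does not call for a redesign.

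**What to change.** 1. In Sweden, classify indication as IBS-C, other recorded indication, or no recorded indication. Count the third level neither as off-label nor as on-label, and give it its own level in the Cox models.
2. Keep all users as the Swedish population. As a sensitivity analysis, show the off-label estimate stratified by the PDR field that Annex 3 B describes as "the practice (primary health care centre or hospital clinic) that issued the prescription".
3. Report the aggregated off-label figure with and without Sweden.
4. In 9.9, replace the expectation that specialist diagnoses suffice with a statement of this bias and its possible directions. State which off-label definition each estimate uses, and reconcile the source-population wording in 9.2.1 with entry by dispensation in 9.2.2.1.

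The cost is one extra category, a few extra table rows, and a Swedish off-label figure that carries a visible unclassifiable share. No new data source is needed, because the issuing-practice field is already described in the protocol.
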